2.3 Benefit/Risk Assessment

The benefit-risk relationship has been carefully considered in the planning of this study. Nonclinical data show that peposertib potently and selectively inhibits DNA DSB repair induced by IR and other DNA damaging agents.

As of 18 December 2019 (Investigator's Brochure, Version 8.0), the important potential risks with peposertib identified for the purpose of the study based on nonclinical studies are as follows:

- Lymphoid depletion with risk of infection
- Stomatitis, mucositis
- Rash
- Increased radiation dermatitis
- Reproductive toxicity
- Increase in liver enzymes: aspartate aminotransferase, alanine aminotransferase and glutamate dehydrogenase
- Drug-drug interactions

Further, the following not important potential risks have been identified:

- Vomiting
- Diarrhea

There are no other important potential risks from completed/ongoing studies that are considered relevant for this rectal study population.

Recommendations for the clinical use of peposertib include the monitoring of adverse effects in the digestive tract and radiation side effects, as well as monitoring of hematological parameters and liver enzymes. In addition, precautionary measures to mitigate the risks of other treatments and treatment recommendations of known adverse reactions, need to be respected when given in combination with peposertib.

More detailed information about the known and expected benefits and risks and reasonably expected AEs of peposertib may be found in Section 4.2 (Scientific Rationale for Study Design)

and the Investigator's Brochure, Participant Information Leaflet, or Development Safety Update Report.

The purpose of this study is to determine whether peposertib can be safely administered in combination with the current neoadjuvant SoC for rectal cancer, capecitabine in combination with RT, and whether the combination with peposertib shows a relevant antitumor efficacy advantage compared with SoC. Improved rates of clinical complete response (cCR) should translate into higher rates of organ preservation in patients with locally advanced rectal cancer. It is hypothesized that this will improve long-term QoL outcomes.

In this study, appropriate precautionary measures to mitigate the potential risks are implemented. The safety will be monitored on an ongoing basis by the SMC. The study will be discontinued in the event of any new findings that indicate a relevant deterioration of the benefit-risk balance for the participants, which would render continuation of the study unjustifiable.

The SoC CRT has a known and well-established toxicity profile. Nausea, vomiting, diarrhea, mucositis, hand-foot syndrome, radiation dermatitis, and decreases in hemoglobin, leucocytes, and platelets, are the most frequently reported Grade 3 AEs in clinical studies with capecitabine and RT (Liu 2016). These potential toxicities can be readily monitored with clinical laboratory, AE, and clinical assessments.

It is known that RT can cause acute toxicities in the form of, e.g. radiation dermatitis and mucositis. Late toxicities arising 3 months or later after the end of RT can be seen in the form of, e.g. mucositis, fibrosis, and bowel perforation. This must be evaluated by appropriate means including physical examination, imaging and endoscopy when indicated. Potentially, acute and late toxicities can be more severe when RT is given in combination with peposertib. This will be evaluated on an ongoing basis.

Based on the available nonclinical and clinical data to date, the conduct of the study, as specified in this protocol, is considered justifiable.

The starting dose of 50 mg once daily peposertib in combination with RT and capecitabine is considered appropriate to mitigate possible AEs by overlapping or unexpected toxicities of the combination, and possible higher formulation-dependent fraction absorbed.

Peosertib has a nonclinical safety profile adequate for the treatment of patients with life-threatening advanced malignancies, and the safety profile does not raise concerns about further investigation of peposertib in participants with cancer. In addition, the available clinical safety data for peposertib when given as a single agent forms a basis for the clinical study in combination with RT, as well as chemotherapy, and supports the investigation also in the neoadjuvant setting.

In conclusion, emerging clinical safety data from studies EMR100036-001 and EMR100036-002, and supportive results of a comprehensive series of nonclinical safety pharmacology, PK, and toxicology studies, as well as primary and secondary PD findings support continued clinical development of peposertib in combination with RT, and/or chemotherapy.

3 Objectives and Endpoints

Study objectives and endpoints are provided in [Table 6](#). Statistical analysis of the endpoints is described in [Section 9.4](#).

Table 6 Study Objectives and Endpoints

Objectives	Endpoints (Outcome Measures)	Endpoints (Outcome Measures) Timeframe
Primary		
To define an MTD and RP2D of peposertib in combination with capecitabine and RT	Occurrence of dose limiting toxicities	Time from first study intervention to the end of CRT with a final assessment at 4 weeks after surgery
Secondary		
To evaluate safety and tolerability of peposertib in combination with capecitabine and RT	
 • Occurrence of TEAEs and treatment-related adverse events according to the NCI-CTCAE version 5.0 • Occurrence of abnormalities (Grade ≥ 3) in laboratory test values, markedly abnormal vital sign measurements, and clinically significantly abnormal ECGs including clinically important increases in QT interval (QTcF) 	Time from first study intervention to final assessment at 1 year
To explore antitumor activity of peposertib in combination with capecitabine and RT	
 • Composite endpoint of pCR/cCR • Disease-free Survival • pCR • cCR • Local recurrence and/or distant metastasis • Neoadjuvant rectal score 	
 • Pathology evaluation of specimen after surgery (pCR) and clinical evaluation 1 to 2 weeks prior to surgery (cCR) • Time from first study intervention to final assessment at 1 year • Pathology evaluation of specimen after surgery • Time from first study Intervention until clinical evaluation 1 to 2 weeks prior to surgery • Time from surgery to final assessment at 1 year • Pathology evaluation of specimen after surgery
To assess the PK of peposertib	PK profile of peposertib in terms of PK parameter estimates (e.g. C _{max} , AUC _{0-t} , t _{max} , CL/f, Vz/f, t _{1/2})	FD1 and FD9

CCI

cCR=Clinical Complete Response, CRT=chemoradiotherapy, CCI [REDACTED]
[REDACTED] ECG=electrocardiogram, FD=fraction day, MTD=maximum tolerated dose, NCI-CTCAE=National Cancer
Institute Common Terminology Criteria of Adverse Events, CCI [REDACTED],
pCR=Pathological Complete Response, PK=pharmacokinetic(s), RP2D=recommended Phase II dose,
RT=radiotherapy, TEAE=treatment-emergent adverse event.

The definition of pathological complete response (pCR) and cCR, and derivation of the pCR/cCR composite endpoint are described in Section 3.1. Statistical aspects of other endpoints are described in Section 9.4.

3.1 Definitions of Pathological Complete Response and Clinical Complete Response, and Derivation of the Composite Endpoint

Pathological Complete Response

Participants are considered to have a pCR if they undergo surgery and no residual cancer is found on histological examination of the removed specimen (ypT₀N₀).

The assessment of pCR will be based on local review of the histology slides.

Clinical Complete Response

Participants are considered to have a cCR if all the criteria below are fulfilled:

- Absence of any residual tumor in the primary site and draining lymph nodes on imaging with magnetic resonance imaging (MRI; T_2 weighted and diffusion weighted) as defined in the [Appendix 5](#), which is based on a modification of tumor evaluation as described by [Maas 2015](#).
- No visible lesion at endoscopy except a flat scar, telangiectasia, and/or whitening of the mucosa (documented by photography)
- Absence of any palpable tumor or irregularity on digital rectal examination (DRE) and endoscopic ultrasonography (EUS) (if indicated or if performed)
- If a biopsy is taken, it must be negative.

[figure not shown]
Composite Endpoint of Pathological Complete Response/Clinical Complete Response

Participants are considered as responders to the composite endpoint pCR/cCR if 1 of the following 2 criteria is fulfilled ([Figure 2](#)):

- Participant had surgery and has pCR
- Participant did not undergo surgery but has cCR (defined above).

Participants who are not operated on and do not undergo the procedures to define cCR will be regarded as nonresponders.

Figure 2 Derivation of Composite Endpoint

cCR=Clinical Complete Response, CR=Complete Response, pCR=Pathological Complete Response, MRI=Magnetic Resonance Imaging. See Section 9.4 for the statistical aspects of the endpoints.

4 Study Design

4.1 Overall Design

This is a multicenter open-label, single arm, dose escalation study in participants with locally advanced rectal cancer.

The study will consist of a Screening period of 4 weeks, a Treatment period of 5 to 5.5 weeks (25 or 28 fraction days [FDs]) (DLT period, see Section 6.6.1), a Short-term Safety Follow-up period of 13.5 weeks including 30 days after surgery, a Long-term Safety Follow-up period until 1 year after the start of study intervention/randomization.

A schematic overview of the study is shown in Section 1.2. A detailed SoA is provided in Section 1.3.

4.1.1 Screening Period

Screening will be performed within 4 weeks prior to FD1 and first day of study intervention administration. Participants will be assessed for eligibility to participate in the study, and will undergo clinical evaluations to ensure compliance with the inclusion and exclusion criteria (Section 5.1 and Section 5.2, respectively). Details of tumor evaluation methods at Screening are provided in Section 8.1.2. Details of rescreening are provided in Section 5.4. For participants who received induction chemotherapy prior to the study, a DRE and endoscopy (and EUS if indicated or if performed per local practice) will need to be done to determine current stage before starting CRT, in compliance with the inclusion criteria (Section 5.1).

4.1.2 Treatment Period

The starting dose of peposertib for the first cohort will be 50 mg once daily (Section 4.3). Participants for next cohorts will be assigned to an peposertib dose determined by the SMC. The SMC dose recommendations will be guided by a Bayesian 2-parameter logistic regression model with overdose control (Appendix 10). The planned cohort size is 3 participants. Peposertib will be given in combination with capecitabine at a dose of 825 mg/m² twice daily and RT of 50 to 50.4 Gy to the tumor area and 45 Gy to the electively irradiated tissues in 25 or 28 fractions (corresponding to 5 to 5.5 weeks). Full details of the dosing regimens are provided in Section 6.6.2.

After each cohort has completed the 5 to 5.5-week treatment period (DLT period), the SMC will review safety, including DLT data, tolerability, and PK data if available, and will recommend the peposertib dose for the next cohort. In addition, any toxicities observed during the Short-term Safety Follow-up will be reviewed and considered by the SMC for the overall evaluation of the safety and proposal of dose escalation of peposertib. Dose limiting toxicities are defined in Section 6.6.1. If the SMC decides to escalate the dose for the next cohort, it is in exceptional cases at discretion of the study team (medical lead and safety lead with input from statistician) to include up to 3 further participants in parallel, on a dose level that has already been tested in a previous cohort.

Participants will receive CRT until treatment completion after 25 or 28 RT fractions or disease progression, unacceptable toxicity or participant refusal to continue.

4.1.3 Follow-up Periods

The study follow-up will include:

- **Short-term Safety Follow-up:** the duration of the Short-term Safety Follow-up is approximately 13.5 to 14 weeks after treatment completion, including 30 days after surgery, with an optional 1 visit per week from Week 7 to Week 14 in case of acute toxicities until recovery to Grade 1 or to baseline. For all participants, a mandatory visit will be performed at Week 14, approximately 1 to 2 weeks prior to surgery, including a tumor assessment with MRI (T_2 weighted and diffusion weighted) needed for restaging and evaluation. Additional details on tumor evaluation methods and response assessments are provided in Section 8.1.2.
- Surgical intervention must be performed 15 weeks (\pm 14 days) after start of study intervention/randomization (i.e. approximately 9.5 weeks after stopping RT), unless there are contraindications for surgery, or if the participant refuses. The last Short-term Safety Follow-up visit is scheduled for Week 19, approximately 4 to 6 weeks after surgical intervention/imaging/biopsy, as per SoC. During this visit, all safety information since the last visit, including surgical and/or biopsy morbidities/toxicities will be collected.
- **Long-term Safety Follow-up:** participants will be followed-up at 21 and 27 weeks after start of study intervention/randomization; every 3 months until 1 year after start of study intervention/randomization. Details on tumor evaluation methods and response assessments are provided in Section 8.1.2. Adjuvant chemotherapy is allowed as per local standards (see Section 6.5). Participants receiving adjuvant chemotherapy will continue to follow the schedule of activities (SoA) as per protocol. If adjuvant chemotherapy is given, any additional safety evaluations/laboratory tests will be as per local practice.
- Participants who have already been followed up for more than 1 year (Long-term Safety or Survival Follow-up) will be discontinued from the study after the approval of protocol amendment version 4.0 by the respective Health Authority and Ethics Boards. Participants will be informed of the discontinuation by the Investigator via a phone call. No further study visits or assessments are planned.

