Peosertib Capecitabine RT		X: Peposertib qd 5 d/wk (only on FD) X: Capecitabine 825 mg/m ² bid 5 d/wk (only on FD) X: RT 1.8 Gy/fraction, 5 FD/wk, integrated concomitant boost (total daily dose 2 Gy) is allowed									Surgery		
Visit Week	-4 to -1	1	1	2	2	3	4	5	5 or 6	7 to 14	15	19	
Visit Day	-28 to -1	FD1	FD2	FD6	FD9	FD11	FD16	FD21	FD25 or FD28/ETT	In case of acute toxicities one visit/wk until recovery ^{a,b}	One visit / wk		If premature discontinuation during treatment, the SoA for FD25/FD28 should be performed. In such cases, this visit will be considered the ETT visit. ^a Where recovery means until the toxicity reduces to Grade 1 or to baseline Wk 14 visit is mandatory. ^b In case of a pandemic, it is per Investigator's discretion if these visits can be done via a phone call. Wk 14 visit remains a clinic visit.
Visit Window (Days)										± 7 for Wk 14 only/± 2 for other visits	± 14	± 14	
Assessments and Procedures													
Serum β-HCG Pregnancy	X									Wk 14 only			If applicable.
Vital Signs	X	X		X		X	X	X	X	X		X	Pulse rate, DBP, SBP, and body temperature. Vital signs during treatment are to be done on a weekly basis, not necessarily on the specified FD

		Evaluation Period											Notes
Study Period	Screening	Treatment Period/DLT Period (peposertib + capecitabine + RT)								Short-term Safety FU			Capecitabine given within 30 min after meal (AM and PM dosing), peposertib given 1 h after meal, RT given 1.5 h (± 30 min) after M3814 dosing. See Table 7 and Section 6.6.2.4.
Study Day	Day -28 to -1	FD1 to 25 or 28 Visits: on all FD (FD1 to FD25 or 28), FD25 or 28 is last RT day											
Peosertib Capecitabine RT		X: Peposertib qd 5 d/wk (only on FD) X: Capecitabine 825 mg/m ² bid 5 d/wk (only on FD) X: RT 1.8 Gy/fraction, 5 FD/wk, integrated concomitant boost (total daily dose 2 Gy) is allowed									Surgery		
Visit Week	-4 to -1	1	1	2	2	3	4	5	5 or 6	7 to 14	15	19	
Visit Day	-28 to -1	FD1	FD2	FD6	FD9	FD11	FD16	FD21	FD25 or FD28/ETT	In case of acute toxicities one visit/wk until recovery ^{a,b}	One visit / wk		If premature discontinuation during treatment, the SoA for FD25/FD28 should be performed. In such cases, this visit will be considered the ETT visit. ^a Where recovery means until the toxicity reduces to Grade 1 or to baseline Wk 14 visit is mandatory. ^b In case of a pandemic, it is per Investigator's discretion if these visits can be done via a phone call. Wk 14 visit remains a clinic visit.

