8.3 Adverse Events and Serious Adverse Events

The definitions of an AE and a serious adverse event (SAE) are in [Appendix 7](#).

8.3.1 Time Period and Frequency for Collecting Adverse Event and Serious Adverse Event Information

The AE reporting period for safety surveillance begins when the participant is initially included in the study (date of first signature of informed consent/date of first signature of first informed consent) and continues until the final assessment at 1 year. Any AE assessed as not related to study intervention will be recorded only up to the short-term safety follow-up period. Any AE assessed as related to study intervention will be recorded up to resolution or permanent outcome, irrespective of the time elapsed since the last administration of study intervention.

Any SAE assessed as related to study intervention must be recorded and reported, as indicated in [Appendix 7](#), whenever it occurs, irrespective of the time elapsed since the last administration of study intervention. Any SAE assessed as not related to study intervention must be recorded and reported, as indicated in [Appendix 7](#), only up to Week 27 in the long-term safety follow-up period.

The method of recording, evaluating, and assessing causality of AEs (including SAEs) and the procedures for completing and transmitting SAE reports are in [Appendix 7](#).

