After each cohort has finished the peposertib treatment period (DLT period), the SMC will review the safety, tolerability, and PK data and will provide recommendations for the next cohort, move to the next dose level, stay on the actual dose level, de-escalate to a lower dose level, or explore alternative schedules of peposertib. In addition, the SMC will review safety, tolerability, and PK data when each cohort has finished the 30-day follow-up period after surgery to provide further recommendations on dose escalation.

Details of structures and associated procedures will be defined in separate SMC charters.

Regulatory and Ethical Considerations

- This study will be conducted in accordance with the protocol and the following:
 - Consensus ethical principles derived from international guidelines, including the Declaration of Helsinki and Council for International Organizations of Medical Sciences (CIOMS) International Ethical Guidelines
 - Applicable ICH GCP Guidelines
 - Applicable laws and regulations.
- The Investigator must submit the protocol, protocol amendments (if applicable), ICF, Investigator Brochure, and other relevant documents to an IRB/IEC and the IRB/IEC must review and approve them before the study is initiated.
- Any protocol amendments (i.e. changes to the protocol) will be documented in writing and require IRB/IEC approval before implementation of changes, except for changes necessary to eliminate an immediate hazard to study participants. When applicable, amendments will be submitted to the appropriate Health Authorities.
- The Investigator will be responsible for the following:
 - Providing written summaries of the status of the study to the IRB/IEC annually or more frequently per the IRB's/IEC's requirements, policies, and procedures
 - Notifying the IRB/IEC of SAEs or other significant safety findings, as required by IRB/IEC procedures
 - Providing oversight of the study conduct at the site and adherence to requirements of 21 CFR, ICH guidelines, the IRB/IEC, European regulation 536/2014 for clinical studies (if applicable), and all other applicable local regulations.
- The protocol and any applicable documentation will be submitted or notified to the Health Authorities in accordance with all local and national regulations for each site.

Emergency Medical Support

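### The schedule does not guarantee the 30 days of post-surgical follow-up that the protocol states, because surgery and the closing short-term safety visit have separate windows, both counted from treatment start

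*Protocol*

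**What the plan says.** - **Length of the period.** Section 4.1 describes "a Short-term Safety Follow-up period of 13.5 weeks including 30 days after surgery". Section 4.1.3 gives approximately 13.5 to 14 weeks after treatment completion and repeats the 30 days.
- **Surgery.** Section 4.1.3: "Surgical intervention must be performed 15 weeks" after the start of study intervention, with a 14-day margin on either side.
- **Closing visit.** Section 4.1.3: "The last Short-term Safety Follow-up visit is scheduled for Week 19, approximately 4 to 6 weeks after surgical intervention". Table 1 gives this visit its own ± 14-day window and makes it the visit at which surgical and post-surgical adverse events are collected.
- **End of the period.** Section 8.2 ends short-term follow-up at Week 19 and contains no surgery-based rule.
- **Recording of adverse events.** Section 8.3.1: "Any AE assessed as not related to study intervention will be recorded only up to the short-term safety follow-up period". The same section follows related events to resolution whenever they occur and records unrelated serious events to Week 27. Table 2 applies the same limits at the later visits.
- **Safety Monitoring Committee (SMC) review.** Appendix 2 sets the post-surgery review "when each cohort has finished the 30-day follow-up period after surgery". Section 9.4.4 and SAP 6.1 instead review each participant's data at about 19 weeks after treatment start.
- **Analyses using the same milestone.** The end of short-term follow-up for the last participant triggers the primary analysis (Section 9.4.4, SAP 6.3) and one of the SAP 6.2 analyses.
- **Delayed surgery is foreseen.** The SAP uses an eCRF page for rectal surgery after Week 15 (Sections 9 and 12.4) and names delayed surgery in a listing (15.2.1).

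**The concern.** The protocol describes the closing visit by its distance from surgery but schedules it by its distance from treatment start. An operation late in its window, or a visit early in its window, shortens post-operative observation, and no rule moves the visit or the recording limit to compensate.

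Study intervention here means peposertib, capecitabine and radiotherapy (Section 6), not the operation. A site may reasonably judge a non-serious wound or other surgical complication unrelated. If it starts after the closing visit but within 30 days of surgery, it is not recorded, and under Table 2 the Week 21 visit does not recover it.

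The all-cause late-toxicity table in SAP 15.2.3 would then combine participants whose post-operative ascertainment differed by weeks. The data available for the post-surgery safety review would vary in the same way.

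**Working it through.** **Inputs.** Surgery: 15 weeks ± 14 days (4.1.3, Table 1). Closing visit: Week 19 ± 14 days (4.1.3, Table 1). Treatment: 5 or 5.5 weeks (4.1). Short-term follow-up: 13.5 to 14 weeks (4.1.3). Days are counted from treatment start.

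**1. The plan's own figure.** Treatment plus follow-up: 5.5 + 13.5 = 19.0 weeks and 5 + 14 = 19.0 weeks, so Week 19 reproduces. The other pairings give 5 + 13.5 = 18.5 weeks and 5.5 + 14 = 19.5 weeks.

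**2. Nominal interval.** 19 × 7 − 15 × 7 = 133 − 105 = 28 days, against the stated 30. The other two pairings give (18.5 − 15) × 7 = 24.5 days and (19.5 − 15) × 7 = 31.5 days.

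**3. Permitted interval.** Surgery may fall on days 91 to 119 and the visit on days 119 to 147.
- Shortest: 119 − 119 = 0 days. Longest: 147 − 91 = 56 days.
- Visit exactly on day 133: 133 − 119 = 14 to 133 − 91 = 42 days. Reaching 30 days needs surgery at least 2 days early, so 16 of the 29 permitted surgery days fall short.

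**4. Count of permitted date pairs.** There are 29 × 29 = 841. The interval is 28 + v − s, with v and s the visit and surgery offsets.
- Under 28 days (v < s): (841 − 29)/2 = 406 pairs, 48%.
- Under 30 days (v − s ≤ 1): 406 + 29 + 28 = 463 pairs, 55%.
- Within 28 to 42 days, the stated 4 to 6 weeks: 39%.

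These are shares of date combinations, not of participants.

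**5. Delayed surgery.** Beyond day 119 the operation can fall after a visit that was itself in window.

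**6. Which events are lost.**

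| Event | Recording ends |
|---|---|
| Related, serious or not | No time limit |
| Unrelated, serious | Week 27, i.e. 189 − 119 = 70 days after the latest in-window surgery |
| Unrelated, non-serious | End of short-term follow-up |

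Only the last row is exposed.

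**7. Where it would show.** The SAP's on-treatment period ends 30 days after the last dose, at about 5 × 7 + 30 = 65 to 5.5 × 7 + 30 = 68.5 days, or 75.5 with the maximum 7-day delay. Surgery starts at day 91. New post-operative events therefore enter through the late-toxicity outputs of SAP 15.2.3, whose main table is not restricted by relationship.

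**The case against.** **The nominal shortfall is trivial.** A reader might infer that the 30 days is missed by design even on the planned dates. That leans too hard on 2 days. Section 4.1.3 uses approximate wording, one pairing of its durations gives 31.5 days, and the 4 weeks after surgery in the Section 3 endpoint timeframe equals the nominal 28 days. This stands; the point rests on the unlinked windows.

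**Surgery was not ignored.** The visit is described by its distance from surgery, and surgical morbidity must be collected at it. A visit at 0 or 14 days would fit Table 1 but contradict that description. This stands as a description of intent, but nothing in the schedule enforces it.

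**There is no single adverse-event cut-off.** A reader might infer that all post-operative events stop at Week 19. Section 8.3.1 does not say so. Appendix 7 also makes clinical Grade 4 or 5 events, and events causing unplanned or prolonged hospitalization, reportable as serious, so many important complications are covered to Week 27.

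**The SMC is not confined to Week 19.** Appendix 2 ties its review to 30 days after surgery. What remains is disagreement with Section 9.4.4 and SAP 6.1.

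**The primary endpoint is not affected.** Section 6.6.1 counts dose-limiting toxicities only to completion of chemoradiotherapy. The primary cut-off also waits for the last participant, so those enrolled earlier will generally have been followed past their own Week 19.

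**The 55% is largely built in.** Two symmetric windows put about half of all pairs below any nominal gap, and in practice a post-operative visit would probably be booked around the operation. This stands; the figure shows what the rules permit.

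**Little can still be changed.** Enrolment is closed and treatment complete. By 6 May 2021, 16 of 19 treated participants had finished follow-up to Week 19. This limits the prospective benefit, but not the need to report the intervals.

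**Conclusion.** The concern holds in a limited form. The permitted interval from surgery to the closing visit is 0 to 56 days, and for delayed surgery the visit can come first. The stated 30 days and 4 to 6 weeks are therefore intentions that the schedule does not secure. The exposed data are non-serious events judged unrelated to study intervention, and the main affected output is the all-cause late-toxicity table. The SMC's post-surgery review also has two definitions.

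The documents do not support a claim that 55% of participants are affected, that related or serious events are lost, or that dose-limiting toxicity results are compromised. How many participants fall short depends on actual surgery and visit dates, which the documents do not give. The range rests on reading the two ± 14-day windows as separate, as Table 1 presents them.

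**What to change.** - **One definition.** Reconcile Protocol 4.1, 4.1.3, Table 1, 8.2, 8.3.1, 9.4.4 and Appendix 2 with SAP 6.1 and 6.3. For operated participants, including those with delayed surgery, end short-term follow-up and recording of unrelated adverse events at the later of the Week 19 visit and 30 days after surgery. Participants without surgery keep Week 19. Use the same date for the SMC's post-surgery review and the primary cut-off.
- **Participants already past Week 19.** Report each surgery-to-visit interval, flag those under 30 days, and show the flag wherever post-operative and late-toxicity data are presented.

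**Cost.** No additional visit is needed. For the latest in-window surgery, 30 days ends on day 119 + 30 = 149, inside the Week 21 window (147 ± 7, days 140 to 154). That is 16 days after the nominal Week 19, so the primary cut-off could move by about two weeks, and by more if surgery is delayed beyond its window. Few current participants are still affected prospectively, so most of the gain lies in reporting the intervals.
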